7.6.5.3 Exploratory Renal Biomarkers

Exploratory renal biomarkers include:

- Urinary biomarkers: kidney injury molecule 1 (KIM-1), liver fatty acid binding protein (L-FABP), 8-OHdG, and N-acetyl- β -D-glucosaminidase (NAG).

- Blood biomarkers: sTNFR1, hs-CRP.

Descriptive statistics for the listed renal biomarkers will be presented by treatment group and by study visit where appropriate.

7.7 Safety

7.7.1 Adverse Events

All AEs recorded on the eCRF will be coded using the MedDRA dictionary Version 20.5 (or a later version if updated during the study) and classified as TEAEs as follows:

TEAEs are events with start date on or after the date of first dose of double-blind study drug and up to 30 days after date of last dose of double-blind study drug.

All AE data will be listed by treatment group. Treatment-emergence status, AEs leading to discontinuation of double-blind study drug, AEs resulting in death, and serious AEs will be presented in the listing.

Summary tables of TEAEs by treatment group and overall will be produced for the Safety population.

The relationship between an AE and study drug is assessed as related or not related.

An overview table will summarize the number and percentage of subjects with at least 1 of the following TEAEs, where subjects with more than 1 TEAE in a particular category are counted only once in that category:

- Any TEAE
- Drug-related TEAE
- Severe drug-related TEAE
- Treatment-emergent SAE
- Treatment-emergent drug-related SAE
- TEAE leading to study drug discontinuation
- Drug-related TEAE leading to study drug discontinuation
- TEAE leading to death

The number and percentage of subjects reporting each AE will be summarized by SOC and PT for the Safety population. Tables will be sorted, as to SOC, by Internationally Agreed Order. PTs will be sorted by PT code (variable PTCD). The following summaries will be produced:

- TEAEs by SOC and PT
- TEAEs by onset time period, SOC, and PT (<28 days; ≥28 days and <56 days; ≥56 days and <84 days; ≥84 days)

- TEAEs by PT
- TEAEs reported by at least 5% of subjects in any treatment group, by SOC and PT
- TEAEs related to treatment, by SOC and PT
- TEAEs related to treatment, by PT
- TEAEs by relationship to treatment, by SOC and PT
- TEAEs by severity, by SOC and PT
- TEAEs related to treatment by severity, by SOC and PT
- TEAEs causing discontinuation from treatment, by SOC and PT
- TEAEs related to treatment causing discontinuation from treatment, by SOC and PT
- Treatment-emergent SAEs, by SOC and PT
- Treatment-emergent SAEs related to treatment, by SOC and PT
- TEAEs leading to death, by SOC and PT
- SAEs during Single-blind, placebo run-in, by SOC and PT

In the above summaries, subjects with more than 1 AE within a particular SOC are counted only once for that SOC. Similarly, subjects with more than 1 AE within a particular PT are counted only once for that PT. For summaries by maximum intensity, subjects with multiple AEs within a particular SOC or PT will be counted under the category of their most severe AE within that SOC or PT.

No statistical comparisons of AE related data between treatment groups will be performed.

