- blood (plasma and serum) and urine sample for biomarkers (the mid-stream, first-morning void urine samples collected by the subjects at home will be used for the analysis of biomarkers)
- treatment-emergent adverse event recording
- concomitant medication review
- vital signs, consisting of supine blood pressure, supine pulse rate, and oral body temperature
- body weight
- resting 12-lead ECG
- physical examination
- PK sampling; see [Section 7.7.1](#)
- assess double-blind compliance

7.5.4.6 *End of Study Follow-up (Visit 7): Visit 6/ET+28 ± 7 days*

The following information and procedures will be recorded and performed for all subjects as part of the follow-up assessments:

- contact IXRS
- pre-Visit 7 call for reminder of urine collection
- urine pregnancy test for female subjects of childbearing potential
- urine sample for UACR (2 consecutive day mid-stream, first-morning void urine samples to be collected at the subject's home on the morning before and the morning of Visit 7)
- complete blood count
- serum chemistry profile (including sUA and serum creatinine to calculate eGFR); see [Appendix A](#) for the evaluations to be performed
- thyroid hormones
- lipid panel

- urinalysis
- blood (plasma and serum) and urine sample for biomarkers (the mid-stream, first-morning void urine samples collected by the subjects at home will be used for the analysis of biomarkers)
- treatment-emergent adverse event recording
- concomitant medication review
- vital signs, consisting of supine blood pressure, supine pulse rate, and oral body temperature
- body weight

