7.6.2.1 Adverse Events

7.6.2.1.1 Definitions

The term "adverse event," as used by the Sponsor, is synonymous with the term "adverse experience," which is used by the Food and Drug Administration.

An AE is any untoward, undesired, unplanned clinical event in the form of signs, symptoms, disease, or laboratory or physiological observations occurring in a human being participating in a clinical study with a Sponsor test article, regardless of causal relationship. This includes the following:

- Any clinically significant worsening of a pre-existing condition.

Note: Emergence of a new pathogen associated with a clinical event during therapy at a site other than the initial site of infection will be considered to be an AE.

- Any recurrence of a historical condition.
- An AE occurring from overdose of a Sponsor study drug whether accidental or intentional (ie a dose higher than that prescribed by a health care professional for clinical reasons).
- An AE occurring from abuse of a Sponsor study drug (ie use for non-clinical reasons).
- An AE that has been associated with the discontinuation of the use of a Sponsor study drug.

Note: A procedure is not an AE, but the underlying cause/reason for a procedure may be an AE.

A ***pre-existing condition*** is a clinical condition (including a condition being treated) that is diagnosed before the subject signs the ICF and that is documented as part of the subject's medical history.

The questions concerning whether the condition existed before the start of the active phase of the study and whether it has increased in severity and/or frequency will be used to determine whether an event is a TEAE. An AE is considered to be treatment-emergent if (1) it is not present when the active phase of the study begins and is not a chronic condition that is part of the subject's medical history, or (2) it is present at the start of the active phase of the study or as part of the subject's medical history, but the severity or frequency increases during the active phase. The active phase of the study begins at the time of the first dose of the study drug. The active phase of the study ends at the follow-up visit.

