6.2 Handling of Dropouts, Missing Data, and Outliers

Missing data will not be imputed for safety analyses. The safety evaluations will be performed on observed data only.

For AEs with partial or missing onset or stop dates:

AE stop date will be imputed first as:

- If stop date is complete missing, assume it is ongoing (no imputation);
- For a partial AE stop date (day is missing, or both day and month are missing): December 31st if both day and month are missing, or last day of the month if only day is missing.

Then AE onset date will be imputed as:

- If onset date is complete missing: the first dose date;
- For a partial AE onset date (day is missing, or both day and month are missing):
 - Partial date < the first dose date: December 31st, or last day of the month
 - Partial date = the first dose date: the first dose date
 - Partial date > the first dose date: January 1st if both day and month are missing, or first day of the month if only day is missing.

If the imputed AE onset date is after the AE stop date/imputed AE stop date, then the onset date will be set to the AE stop date/imputed AE stop date.

The imputed dates will not be listed. Study day relative to the first dose of double-blind study drug associated with missing or partial dates will not be displayed in AE listings.

In the event that a partial date (month/year or year) for concomitant medication is available, this information will be used as follows:

- When both month and year are available – first day of the month will be used for start date and the last day of the month will be used for the stop date.
- When only year is available – January 1st will be used for the start date and December 31th will be used for the stop date.

The imputed dates will only be used to determine whether a concomitant medication will be classified as prior medication or concomitant medication.

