7.9 Interim Analysis

No interim analysis is planned for this study.

8. Changes in Planned Analysis

Not applicable.

Statistical Analysis Plan

Teijin America, Inc.
TMX-049DN-201

9. References

The schedule of study procedures (from the Protocol) is attached for reference.	Screening		Single-Blind, Placebo, Run-in Phase		Double-Blind Treatment Phase				Follow-up
	Visit 1	Visit 2		Visit 3	Start of study drug	Visit 4	Visit 5	Visit 6/ET	Visit 7
Study days and visit window guidelines	Day -42 to Day -15	Day -14 ± 4 days	Day -14 ± 4 days to Day 0	Day 0	Day 1	Day 14 ± 4 days	Day 42 ± 7 days	Day 84 ± 7 days	Visit 6/ET+28 ± 7 days
Administrative Procedures									
Informed consent	X								
Assignment of Screening number	X								
Contact IXRS	X	X		X		X	X	X	X
Check of eligibility based on inclusion/ exclusion criteria	X	X		X					
Assignment of randomization number				X					
Pre-visit telephone reminder for urine and PK ¹		X		X		X	X	X	X
Trial Compliance									
Prior/concomitant medication review	X	X		X		X	X	X	X
Dispense urine collection supplies	X	X		X		X	X	X	
Investigational Product									
Dispense study drug (placebo) for single-blind run-in		X							
Administration of placebo			qd dosing for 2 weeks						
Assess single-blind compliance				X					
Dispense double-blind study drug (placebo or TMX-049)				X		X	X		
Administration of TMX-049 or placebo						qd dosing for 12 weeks			
Assess double-blind compliance						X	X	X	
Clinical Procedures/Assessments									
Demographics and medical history	X								
Height	X								
Body weight	X			X		X	X	X	X
Vital signs (blood pressure ² , pulse rate, and body temperature)	X	X		X		X	X	X	X
Physical examination		X						X	

Statistical Analysis Plan

Teijin America, Inc.
TMX-049DN-201

The schedule of study procedures (from the Protocol) is attached for reference.	Screening		Single-Blind, Placebo, Run-in Phase		Double-Blind Treatment Phase				Follow-up
	Visit 1	Visit 2		Visit 3	Start of study drug	Visit 4	Visit 5	Visit 6/ET	Visit 7
Study days and visit window guidelines	Day - 42 to Day - 15	Day - 14 ± 4 days	Day -14 ± 4 days to Day 0	Day 0	Day 1	Day 14 ± 4 days	Day 42 ± 7 days	Day 84 ± 7 days	Visit 6/ET+28 ± 7 days
12-lead ECG		X						X	
AE monitoring	X	X	X	X					
TEAE monitoring					X	X	X	X	X
Laboratory Assessment									
UACR ³	X								
First morning void UACR		X ⁴		X ^{4,5}		X ^{4,5}	X ^{4,5}	X ^{4,5}	X ^{4,5}
Complete blood count (CBC)	X			X		X	X	X	X

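### SAP 7.7.1 drops the protocol's worsening limb from the TEAE definition, so a pre-dose AE that worsens on treatment but keeps its original record and start date would be missing from the double-blind AE tables

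*SAP*

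**What the plan says.** **Protocol 7.6.2.1.1** gives two routes to treatment-emergent status. The first is an event not present when the active phase begins. The second is an event present at that point, or in the medical history, "but the severity or frequency increases during the active phase". The phase starts at first dose of study drug, which Table 2 places on Day 1, and "The active phase of the study ends at the follow-up visit". Table 2 and protocol 7.5.4.6 time that visit at "Visit 6/ET+28 ± 7 days".

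**SAP 7.7.1** has one route: "TEAEs are events with start date on or after the date of first dose of double-blind study drug and up to 30 days after" the last double-blind dose. Severity and frequency play no part.

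**AE tables.** SAP 7.7.1 builds its AE summaries from TEAEs. The one exception is "SAEs during Single-blind, placebo run-in, by SOC and PT", which is not a double-blind table. All AEs are listed, with treatment-emergence status shown.

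**Changes.** SAP section 8 reads as not applicable, and the version history lists no change to 7.7.1.

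**The concern.** Safety and tolerability is a stated objective, and AE incidence reaches the reader only through the TEAE tables. AEs are collected from consent (protocol 7.6.2.1.2), and the pre-randomization visits may take up to 6 weeks (protocol 7.1), so some subjects can start double-blind drug with an AE in progress.

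If such an AE goes from mild to severe on treatment, the protocol calls it treatment-emergent. Under the SAP's rule it is not, as long as it keeps its original start date. It would then be missing from the tables of overall incidence, severity, relatedness, AE-related discontinuation and the 5% listing by term. The worsening limb exists to count such events. The same AE would be classified differently by two governing documents, with no departure declared.

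**Working it through.** No published figure needs reproducing. The check compares the two definitions and then sizes the difference.

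**1. Which events are classified differently**

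| Event | Protocol 7.6.2.1.1 | SAP 7.7.1 |
|---|---|---|
| New onset, first double-blind dose to last dose + 30 days, by Visit 7 | TEAE | TEAE |
| Condition diagnosed before consent, clinically significant worsening on treatment | TEAE; the worsening is itself an AE | TEAE, by its own start date |
| AE starting between consent and first dose, worsens, new dated record | TEAE | TEAE |
| AE starting between consent and first dose, worsens, original record kept | TEAE | Not a TEAE |
| New onset after day 30 and by Visit 7 | TEAE | Not a TEAE |
| Subject without Visit 7 | Collection ends at day 28 (7.6.2.1.2) | Inside 30 days, nothing lost |

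Only the fourth and fifth rows differ.

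**2. Does anything else in the SAP restore the fourth row?** The date rules in SAP 6.2 deal with missing or partial stop dates and then with onset ("Then AE onset date will be imputed as"). They do not address a dated change in severity. The run-in SAE table would hold a serious event of this kind, but not a non-serious one. The disposition summary in SAP 7.2 would still show a discontinuation and its primary reason, but it is not an AE table.

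**3. Size of the fourth row.** The documents give no rate, so both ranges are assumptions: 5% to 20% of subjects have a pre-dose AE, and 5% to 20% of those worsen without a new record.

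- All subjects: 132 × 0.05 × 0.05 = 0.3; 132 × 0.20 × 0.20 = 5.3.
- Per arm, 132 / 3 = 44: 44 × 0.05 × 0.05 = 0.1; 44 × 0.20 × 0.20 = 1.8.
- One subject is 1/44 = 2.3 percentage points of an arm.
- The table defined by "TEAEs reported by at least 5% of subjects in any treatment group, by SOC and PT" has a threshold of 0.05 × 44 = 2.2 subjects. A term falling from 3/44 = 6.8% to 2/44 = 4.5% would leave it if no other arm reached 5%. It would stay in the tables without a threshold.

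**4. Size of the fifth row.** Visit 7 falls 21 to 35 days after Visit 6/ET. With last dose on the Visit 6 day, days lost = max(0, day − 30).

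- At the day-28 target: 0. At the latest on-schedule day: 35 − 30 = 5 (6 if the last dose is the day before Visit 6).
- Visits spread evenly over the 15 days (assumed): (1+2+3+4+5)/15 = 1.0 day; over 84 + 28 = 112 days, 1.0/112 = 0.9%.
- Triangular weights 8 − |day − 28|, sum 64 (assumed): (5×1 + 4×2 + 3×3 + 2×4 + 1×5)/64 = 35/64 = 0.55 day; 0.55/112 = 0.5%.

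**The case against.** **The loss depends on a form we cannot see.** If sites enter a worsened AE as a new dated record, the SAP rule counts it. There are signs that they might. Table 2 separates AE monitoring before dosing from "TEAE monitoring" from Day 1, and protocol 7.5.4 tells sites to record treatment-emergent events at Visits 4 to 7. Under the protocol's own definition a worsened pre-dose AE is such an event. SAP 7.7.1 also expects several AEs per subject within one preferred term. This stands as a limit on the consequence. It does not settle the matter, because neither document states that a new record is opened, and the SAP's definition still differs from the protocol's.

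**The 30-day window is defensible.** Half-life in the Phase 1 study of doses up to 380 mg was 10 to 19 hours, so day 30 is at least 720/19 ≈ 38 half-lives after last dose. Protocol 7.1 and SAP 2.2 put Visit 7 at 4 weeks after last dose, inside the window. This largely stands: the end point needs aligning or declaring, and is not a fault in itself. A reader might infer that the schedule attached to the SAP contradicts its 30-day rule by marking "TEAE monitoring" at Visit 7. The schedule shows when sites ask about events and does not define the term.

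**No inference is at stake.** AE data are not compared statistically between arms, all AEs are listed, and expedited SAE reporting is untouched. This also stands.

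**Conclusion.** The SAP's TEAE definition departs from the protocol's, and the departure is not declared. The consequence is conditional: an AE that begins between consent and first double-blind dose, worsens on treatment and keeps its original record would be absent from all double-blind AE incidence tables. The number is unknown and probably small. The 0.3 to 5.3 subjects out of 132 rest on assumed rates. Descriptive counts alone are affected.

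Three stronger readings are tempting and not supported:

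- That worsened pre-dose AEs will be left out. This requires that no new record is opened, which the documents do not say.
- That worsening of medical history is lost too. Clinically significant worsening of a condition diagnosed before consent is itself an AE under protocol 7.6.2.1.1, with its own start date.
- That the 30-day cut loses a material amount of safety data. On schedule it is 0 days at the target and at most about 5. It could be longer if an early termination visit falls well after the last dose. The events stay in the listings.

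**What to change.** **Main change.** In SAP 7.7.1, add that an AE with onset before first double-blind dose is also treatment-emergent if it becomes more severe or more frequent on or after that dose, within the treatment-emergent period. State whether the eCRF identifies this by a dated severity change or by a new AE record, and write the derivation to match.

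**Minor change.** Either end the period at Visit 7, as the protocol does, or keep the uniform 30-day window and declare the departure in section 8.

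**Cost.** A few lines of SAP text and one derivation, with slightly higher counts. The derivation depends on what the eCRF captures: with one severity per AE and no dated change, it cannot be programmed without a data-entry convention or extra collection, so check this first. Ending at Visit 7 makes the window vary by subject, which the 30-day option avoids.

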7.6.2.2.1 Reporting Serious Adverse Events

Reporting of SAEs will be conducted in accordance with the appropriate regulatory guidelines. All SAEs that occur from the time of consent to the Follow-up Visit (Visit 7) must be reported in an expedited manner, whether or not the event is considered to be associated with the study drug.

Investigators will send the SAE report by fax or email to [REDACTED] immediately (within 24 hours) of becoming aware of an SAE. Covance PV&DSS will follow-up with the site in case of delayed SAE report.

[REDACTED]

The Investigator must also provide with urgent priority (upon receipt of a request) other relevant documentation (eg copies of diagnostic test results, hospital discharge summary, and/or autopsy report) and send this information by fax or email to [REDACTED].

All SAEs must be recorded in the subject's source documentation and documented in the CRF. Medications administered in association with an SAE must be documented in the CRF and in the subject's source documentation. The Investigator must also promptly notify the IRB of SAEs, including any follow-up information, in accordance with the local institutional policy and applicable regulatory requirements. Regulatory authorities will be notified of any AE associated with the use of the study drug that is both serious and unexpected, in accordance with the appropriate local regulatory guidelines. Notification of the event will be made by written, expedited safety report.

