7.10.2 Subject Populations Analyzed

The **All Subjects Population** will consist of any subjects who enrolled in the study (signed informed consent) and had study assessments recorded on the database as per the protocol.

The **Safety Population** will consist of all randomized subjects who received at least one study medication tablet or capsule.

The **Modified Intention-to-Treat (mITT) Population** will be used for the efficacy analysis and will consist of all subjects according to their randomization scheme regardless of whether they experienced protocol deviations. The last post randomization UACR will be carried forward (LOCF) for subjects who did not have a Week 12 UACR determination. Randomized subjects with no post randomization UACR will be excluded from the mITT analysis.

The **Per Protocol Population** will be used as a sensitivity analysis for the primary efficacy endpoint and will consist of all subjects according to their randomization scheme who experienced no major protocol deviations.

The **PK Population** will consist of all subjects who received at least one dose of TMX-049 and have evaluable PK data.

All protocol deviations that occur during the study will be considered prior to database lock for their severity/impact and will be taken into consideration when subjects are assigned to analysis populations. Details of subject assignment to the analysis populations will be listed.

Efficacy will be analyzed using the mITT Population (primary analysis) and the Per Protocol Population (supportive analysis), and safety will be analyzed using the Safety Population. Changes from Baseline will utilize values obtained at Visit 3 (the randomization visit) except for the change from baseline in UACR.

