7.10.4.4 Statistical Analysis of Safety

Safety evaluation will include incidence of AEs (or TEAEs), laboratory test results, vital signs, ECG results, and physical examination findings. All summaries of safety data will be based on the Safety Population. No formal statistical analysis of the safety data will be performed. There will be safety summary tables produced and no modeling of data.

Summary tables will be provided for all AEs by treatment group. The incidence of AEs, AEs related to study medication, SAEs, and AEs leading to discontinuation of the study treatment will be presented by MedDRA (Medical Dictionary for Regulatory Activities) system organ class (SOC) and preferred term. In addition, the incidence of AEs by severity will be presented by SOC and preferred term.

The AE summary tables will include counts of subjects. Therefore, if a subject experiences more than 1 episode of a particular AE, the subject will be counted only once for that event. If a subject has more than 1 AE that is coded to the same preferred term, the subject will be counted only once for that preferred term. Similarly, if a subject has more than 1 AE within a SOC, the subject will be counted only once in that SOC.

Laboratory test variables will be summarized by treatment group and visit using descriptive statistics (number of subjects, mean, SD, minimum, median, maximum, as well as mean change from Baseline, and number and percent of subjects within specified categories). Shift tables (ie cross-tabulations of below the lower limit of the normal range, within the limits of the normal range and above the upper limit of the normal range at Baseline versus scheduled visits) will be presented by laboratory test. Laboratory tests with categorical results that cannot be analyzed by change from Baseline or shift table analysis will not be included in these summaries, but will be listed. Data obtained from laboratory tests not required by the

protocol will not be summarized, but will be listed.

Descriptive statistics of vital signs and ECG results at each visit will be presented by treatment group. Physical examination findings will be listed for each subject.

No inferential safety statistical analysis will be performed.

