3.3 Safety Variables

The safety endpoints include:

- Proportion of subjects with reported adverse events (AEs), discontinuation due to AEs and serious adverse events (SAEs)
- Proportion of subjects with AEs considered by the Investigator to be related to study drug
- Proportion of subjects with mild, moderate, or severe AEs as assessed by the Investigator
- Changes from Baseline in vital signs, ECGs, and laboratory parameters

4. Pharmacokinetic/Pharmacodynamic variables

The Pharmacokinetic endpoint is the plasma concentrations of TMX-049 at Study Weeks 2, 6, and 12/ET.

5. Analysis populations

Unless otherwise specified, all efficacy analyses will be performed using the modified Intention-to-Treat (mITT) population, all sensitivity analyses will be

performed using the Per Protocol (PP) population and safety analyses will use Safety population. Pharmacokinetic (PK) analyses will be performed using the PK population.

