5.3 Safety Population

All randomized subjects who received at least 1 dose of study drug will be included in the Safety population. Safety subjects are analyzed according to their actual treatment received.

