7.2 Subject Disposition and Data Sets Analyzed

Subject disposition will be listed and summarized by treatment group, and will include the number and percentage of subjects:

- Screened
 - Entered single-blind Placebo run-in period
 - Discontinued single-blind Placebo run-in period
-

- Randomized
- Treated
- Included in each study population (All subjects, Randomized, mITT, Safety, PP, and PK)

The number and percentage of subjects who complete the study and those who discontinue early (including a breakdown of the primary reasons for discontinuation), will be presented for the subjects randomized in each treatment group.

A summary of subject enrollment by site will be provided by treatment group and overall. A summary of subject randomized by randomization strata (sUA and UACR levels) will also be provided by treatment group.

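### The run-in SAE table is tied to the Safety population, so an SAE in a subject who was never randomised cannot appear in it

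*SAP*

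**What the plan says.** SAP 7.7.1 sets the population for its adverse event tables in one sentence: "The number and percentage of subjects reporting each AE will be summarized by SOC and PT for the Safety population". Fifteen summaries are then listed. Fourteen concern treatment-emergent events; the fifteenth is "SAEs during Single-blind, placebo run-in, by SOC and PT".

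SAP 5.3 defines the population: "All randomized subjects who received at least 1 dose of study drug will be included in the Safety population". Protocol 7.10.2 defines it in nearly the same way; it "will consist of all randomized subjects who received at least one study medication tablet or capsule".

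The general rules point the same way. The opening of SAP section 5 says that, unless something else is specified, "safety analyses will use Safety population". Protocol 7.10.4.4 is firmer: "All summaries of safety data will be based on the Safety Population". Neither document makes an exception for the run-in table, and none of the populations in SAP 5.1 to 5.6 is defined by entry into the run-in.

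The data themselves are gathered. Protocol 7.6.2.2.1 states: "All SAEs that occur from the time of consent to the Follow-up Visit (Visit 7) must be reported in an expedited manner". The disposition summary in SAP 7.2 counts subjects who entered the run-in and has a row for "Discontinued single-blind Placebo run-in period".

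**The concern.** The table describes a period before randomisation, but its population is defined by having got through that period. A subject who has an SAE during the run-in and is then not randomised drops out of both the numerator and the denominator. The loss need not be haphazard, because a serious event is one of the things that can stop a subject from being randomised. The table could then show fewer run-in SAEs than occurred, and its percentages would refer to a group other than the subjects who took run-in placebo. A reader of the study report would reasonably take a table with this title to cover everyone who entered the run-in.

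**Working it through.** The plan states no figure to reproduce. The check consists of following the table to its population and asking which subjects can be counted.

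**1. Order of events.** Placebo run-in dosing starts the day after Visit 2. Randomisation is at Visit 3, after the 2-week run-in (Protocol 7.1 and 7.5.4.2). Everyone in the run-in is therefore not yet randomised, and some never will be: Protocol 7.5.4.2 withdraws subjects who fail eligibility or run-in compliance.

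**2. Who can be counted.**

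| Run-in entrant | Can be in the Safety population? | Run-in SAE can enter the table? |
|---|---|---|
| Randomised and dosed with double-blind drug | Yes | Yes |
| Randomised, no double-blind dose | No, if study drug means double-blind drug | No, on that reading |
| Not randomised | No | No |

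The third row does not depend on how the dosing condition is read. Even if run-in placebo counted as study drug, both definitions still require randomisation.

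**3. Can an SAE cause non-randomisation?** The protocol gives three routes, and a fatal event needs none of them.
- Eligibility is checked again at Visit 3 (Protocol 7.5.4.2).
- Exclusion 33 (Protocol 7.3.2) covers any clinical condition that, in the Investigator's opinion, raises risk or impedes completion of the study.
- Inclusion 7 (Protocol 7.3.1) requires at least 80% compliance in the run-in. With a nominal 14 doses, three missed doses give 11/14 = 78.6%, which fails. A short hospital stay could be enough.
- A subject who dies in the run-in cannot be randomised, so a fatal run-in SAE is always left out.

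**4. Do other planned outputs show these events?** The other summaries in SAP 7.7.1 are of TEAEs, which start on or after the first double-blind dose, so they exclude run-in events. The AE listing covers all AE data and identifies serious events and deaths, so it probably does show them. It is arranged by treatment group, however, and the labels in SAP 7.1 are Placebo, 40 mg, 200 mg and Overall, with none for a subject who was not randomised.

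**5. Size.** The share of omitted subjects is exact in one respect: none of the SAEs in non-randomised entrants can appear. The number is unknown, because the documents give no run-in failure rate and no SAE rate. The following rests wholly on assumed inputs and serves only to show the order of magnitude.
- Assume 10% to 30% of entrants are not randomised. Entrants = 132/(1 − f), so 132/0.9 = 147 to 132/0.7 = 189.
- Assume 1% of entrants have a run-in SAE: 1.5 to 1.9 subjects.
- Assume 50% to 90% of those subjects are not randomised. Omitted: 0.5 × 1.47 = 0.7 to 0.9 × 1.89 = 1.7 subjects.

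**The case against.** The strongest reply is that the population is read from the table's position in a list. The item names no population itself, it is the only one of the fifteen that is not about treatment-emergent events, and SAP 7.1 allows table shells, which are not in the documents, to set other denominators. A shell might already use run-in entrants. That is possible, but three written rules (SAP 7.7.1, the default in SAP section 5, and Protocol 7.10.4.4) all lead to the Safety population and none makes an exception. If a shell does differ, the text still needs to agree with it.

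The second reply is that nothing is lost. SAEs are recorded from consent, reported in an expedited manner and probably listed, and with so few cases a listing tells the reader more than a percentage table. This stands, and it limits the point to the summary table.

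Several stronger readings are tempting, and the documents do not support them.
- *The treatment-group layout proves that non-randomised subjects are excluded.* It does not. SAP 7.2 also describes disposition as summarised by treatment group, yet includes screened subjects and run-in discontinuations. The exclusion follows from the population definition, not from the columns.
- *Only mild or brief SAEs remain in the table.* No rule bars a subject because of a run-in SAE as such, and a substantial event could resolve before Visit 3.
- *The trial loses its only pre-treatment SAE background.* Collection starts at consent, so the run-in is not the only pre-treatment period with SAE data, and no planned analysis uses a run-in rate.
- *The displayed rate is too low by a known amount.* Any such figure comes from assumed inputs.

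**Conclusion.** Wrong as written, minor severity. Under the stated rules, the table omits every SAE in a run-in entrant who was not randomised, and its percentages do not use run-in entrants as the denominator. That conclusion rests on the text alone, with the one proviso that unseen table shells might specify otherwise. That the table can understate run-in SAEs follows from the routes by which an SAE can prevent randomisation; how strongly it does so cannot be computed from the documents. The omission is probably a few subjects at most, and that is a judgement, not a result. Data capture and safety reporting are intact. A reader might infer that the drug's safety comparison is compromised, but AE comparisons are descriptive, between randomised groups, and start at the first double-blind dose, so neither they nor any efficacy endpoint is touched.

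**What to change.** - In SAP 7.7.1, take the run-in SAE table out of the Safety-population list. Produce it on all subjects who entered the single-blind run-in, with the SAP 7.2 count as denominator, in one overall column with rows for later randomised and not randomised. The All Subjects population of SAP 5.1 is too wide for this, since it takes in every consented subject with recorded assessments, whether or not the run-in was entered.
- Add a Not randomised label to the AE listing.
- State this table as an exception to the rule in Protocol 7.10.4.4 that all safety summaries use the Safety Population, and record it in SAP section 8, which at present declares no changes.

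The cost is a few lines of SAP text, one re-specified table and one listing label. No new data are needed, because SAEs are collected from consent and run-in entrants are already to be counted.
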